### 7.1 Dosing Summary

Treatment duration and study duration will be derived as stated in Section 5.3 and summarized using descriptive statistics.

The maximum dose level (8 mg/kg BID, or 12 mg/kg BID) reached by each subject will be summarized according to the Dosing Compliance CRF as a frequency distribution. The number of missed doses as defined in Section 5.3 will be summarized. The number of missed doses will only be defined prior to discontinuation of treatment.

### 7.2 Adverse Events

Adverse events will be recorded from the time of first dose of IMP until Follow-up (Visit 17). Adverse events summaries will only consider treatment emergent adverse events (TEAEs). TEAEs are defined as those adverse events that occurred after the administration of the first dose of study drug. If it cannot be determined whether the adverse event is treatment emergent due to missing or incomplete (partial) onset dates, dates will be imputed for the purposes of determining treatment emergence as described in Section 5.2.1.

Verbatim terms entered into the clinical database via the EDC system will be mapped to preferred terms and system organ classes using version 24.0 of MedDRA.

Summaries that are displayed by SOC and PT will be ordered by descending order of incidence of SOC and PT within each SOC. Adverse event summaries of the following types will be presented for the Safety Population:

- Overall summary of the TEAEs which contain an overview of each item below.
- Subject count and incidence rate of TEAEs and total number of unique TEAEs by MedDRA system organ class and preferred term.
- Subject count and incidence rate of TEAEs by MedDRA preferred term and greatest intensity. Intensity is defined by three categories: "Mild", "Moderate", and "Severe." At each level of subject summarization, a subject is classified according to the greatest intensity if the subject reported one or more events. Adverse events with missing intensity will be considered severe for this summary.
- Subject count and incidence rate of TEAEs by MedDRA preferred term and closest relationship to study drug (Related/Not Related). At each level of subject summarization, a subject is classified according to the closest relationship if the subject reported one or more events. Adverse events with missing relationship will be considered related for this summary.
- Subject count and incidence rate of Serious TEAEs by MedDRA SOC and PT.
- Subject count and incidence rate of TEAEs by dose level, SOC, and PT.
- Subject count and incidence rate of related TEAEs by dose level, SOC, and PT.
- Subject count and incidence rate of TEAEs leading to withdrawal of study medication by MedDRA SOC and PT.
- Subject count and incidence rate of TEAEs leading to dose modification (defined as dose increased, dose reduced, or dose interrupted on the CRF) by MedDRA SOC and PT.
- Subject count and incidence of TEAEs with an outcome of death by MedDRA SOC and PT.

A separate listing of related TEAEs will be generated.

## 7.3 Clinical Laboratory Evaluations

Blood will be collected at Visit 1 (Screening), Visit 3 (Week 0), and Visit 13 (End of Treatment). Urine samples will be collected at all visits. Laboratory parameters (chemistry, hematology, urinalysis) will be presented in data listings. Abnormal values will be flagged as high or low relative to normal ranges, where applicable, by the laboratory vendor.

Change from baseline in quantitative laboratory parameter values will be summarized using descriptive statistics at all visits.

For those laboratory tests in which normal ranges are available, shifts from baseline will be presented. Categories for the shift tables will be high, normal, and low.

Laboratory parameters will be classified according to the categories given by the laboratory vendor. The laboratory parameters from the vendor listed below will be assigned to the following categories for data summaries.

Chemistry	Hematology	Urinalysis
Bun/Creatinine Ratio	PT/INR/APTT	Microalbumin, UR
EGFR (Bedside Schwartz)		Random
Hemoglobin A1C		Urine Chemistry
Pregnancy, qualitative		
Thyroxine, Free		
Triiodothyronine, Free		
TSH Ultrasensitive		
Urine Drug Screen w/ Con		

### 7.4 Physical and Neurological Examination

The physical examination will be conducted at all in-clinic visits. The exam will note Normal and Abnormal readings. For each abnormal reading, clinical significance will be determined. The physical exam procedure will include the following organ systems: Head, ears, eyes, nose, and throat; Skin; Cardiovascular; Respiratory; Gastrointestinal; Genitourinary (as appropriate or indicated); Musculoskeletal; and Allergies. The exam will include an assessment for sign of bladder or kidney pathology including an exam of the abdomen and both flanks. Assessment of edema will also be done. Exam may include suprapubic exam (bladder palpation) if decreased urine output is noted.

A neurological examination will be conducted at all in-clinic visits. A standard neurological exam will be conducted to include an evaluation of mental status, cranial nerves, motor exam, sensory exam, cerebellar (coordination, gait), and reflexes.

A modified version of the physical and neurological exams will be done by a physician via telemedicine at the remote visits. As part of the in-home visit, the nurse will conduct a targeted physical exam including assessment of general appearance, an abdominal and a costovertebral angle tenderness exam, assessment for signs of cystitis, and an assessment of edema. Exam may include suprapubic exam (bladder palpation) if decreased urine output is noted.

All examination results will be reported as normal or abnormal. Clinical significance will be determined for abnormal results.

The results of all examinations will be presented in data listings.

### 7.5 Ophthalmology Assessment

A comprehensive ophthalmological exam will be undertaken at Screening (Visit 1) and End of Treatment (Week 13, Visit 16). Routine visual inspection of each eye was undertaken at in-clinic Visit 5 (Week 2) and Visit 9 (Week 6) for subjects enrolled under protocol version 2.0, 2.1 and 2.2. At these interim visit exams, an exam with dilation may be done if abnormalities are present or the assessment is indeterminate, or as deemed necessary by the ophthalmologist, Medical Monitor or Principal Investigator. The complete exam conducted at Visit 1 and Visit 16 could include up to 2 attempts at assessments of estimated visual acuity, dilated refractive error measurement, dilated slit lamp examination of the lens, and a dilated fundus examination.

The results will be presented in data listings.

### 7.6 Vital Signs

Weight, blood pressure (systolic and diastolic in mmHg), heart rate (bpm), respiratory rate (rpm), and body temperature (°C) will be collected at the Screening visits (Visit 1 and 2) and all post-baseline study visits. Ideally, vital signs will be taken after the subject has been seated for 5 minutes. The initial blood pressure reading will be summarized in the table. Height will be taken at the Screening visit (Visit 1), Visit 3 (Week 0), and End of Treatment (Week 13, Visit 16).

Summary statistics for each measurement and the change from baseline will be presented at each post-baseline visit. All vital sign measurements will be presented in data listings. A separate table and listing will be provided for blood pressure.

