5.5 Preclinical Data

5.5.1 Overview of Pharmacology and Toxicology Findings

A battery of safety pharmacology and toxicology studies conducted *in vitro* and *in vivo* in mice, rats and dogs has been conducted, providing safety support for the progression of the drug Phase 2 clinical trials. The nonclinical safety studies suggest that NNZ-2591 is unlikely to have adverse effects in humans in the cardiovascular system, nervous system, or respiratory system, nor in skeletal, motor, or reproductive function. NNZ-2591 has been tolerated in repeat-dose toxicology studies at doses up to 2000 mg/kg/day in juvenile rats and 400 mg/kg/day in adult dogs for 14 days and up to 400 mg/kg/day in juvenile rats and 120 mg/kg/day in adult dogs for 13 weeks.

Studies of NNZ-2591 in juvenile animals have demonstrated a favorable safety profile. In a 13-week study in juvenile rats there were no NNZ-2591-related adverse effects

In the 14-day study in adult dogs as well as the 13-week studies in adult dogs and juvenile rats, there was a decrease in body weight and food consumption in high dose animals that resolved during the 4-week

recovery period. High dose dogs showed an increase in abnormal feces which again resolved during the recovery period.

In vitro metabolism studies have shown NNZ-2591 to be highly stable to metabolism in human hepatic microsomes, hepatocytes and human plasma. NNZ-2591 has also been shown not to be significantly metabolized by human CYP450 enzymes. *In vivo* studies in rats have shown NNZ-2591 to be excreted primarily (>99%) via the kidney with less than 0.3% in bile and feces. These results confirm that metabolism is not a significant route of elimination.

In vitro cell permeability and in vivo PK studies have shown NNZ-2591 to be approximately 100% orally bioavailable, and NNZ-2591 has demonstrated the ability to cross the blood brain barrier.

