8.1 Inclusion Criteria

To be eligible for this study, participants must meet all of the inclusion criteria and none of the exclusion criteria. Inclusion criteria include:

- 1. Clinical diagnosis of PTHS with a documented disease-causing genetic etiology for the disorder.
- 2. Males or females aged 3 to 17 years at Screening, inclusive.
- 3. Body weight of 12 kg or higher at Screening. Weight measurements may be repeated during the Screening period in consultation with the Medical Monitor.
- 4. Participants with a Clinical Global Impression Severity (CGI-S) score of 4 or greater at the Screening visit.
- 5. Not currently actively undergoing regression or loss of skills defined as no persistent loss of previously acquired developmental skills for a period within 3 months of the Screening visit.
 - a. Previously acquired skills include any skill established and used on a daily basis for at least 3 months.
 - b. Variations in use of skills that is part of a general pattern of ups and downs, as determined by the investigator, are not counted as regression.
 - c. Skills may include language, non-verbal communication, fine motor skills, ambulation (including gait, coordination, independence of walking/standing), social skills, play, self-help.
- 6. Each participant must be able to swallow the IMP provided as a liquid solution.
- 7. The participant's caregiver(s) must have sufficient English language skills to complete caregiver assessments in English.

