For simulation of exposure for children 3-17 (the planned age group for the Phase 2 study), the Centers for Disease Control and Prevention (CDC) Growth Individual charts with 3rd and 97th percentiles (3rd, 10th, 25th, 50th, 75th, 90th, and 97th) were downloaded from the CDC.gov website. The body weights for boys and girls from 36.5 months (3 years) to 17 years old (203.5 months) inclusive were combined for the input to Phoenix WinNonLin as a csv file. The file contained columns for 3rd, 5th, 10th, 25th, 50th, 75th, 90th, 95th, and 97th percentiles for each month of age and gender individually. Column with gender was added for the combined dataset. Age groupings for the allometric scaling analysis were Group 1 (3 to < 6), Group 2 (6 to < 12), and 12-17.

The equation for allometric scaling was implemented in the Data Wizard function of Phoenix WinNonLin using weight for children of different age, gender, and percentile as direct input.

Doses were varied in the range from 11 to 20 mg/kg for final estimate with 1 mg/kg increments. The dose levels 11, 12, 13, 14, ... 20 mg/kg were used to calculate the related exposures for different body weight values and compare the resulting AUC_{tau} values with adult results.

[figure not shown]
Additionally, a 17.5-mg/kg dose was evaluated for the lowest body weights. Preliminary evaluation of suitable doses was done starting from 3 mg/kg dose levels. The parameters derived for this allometric scaling were AUC_{tau} at steady state to compare with adult exposures.

2. Allometric Scaling Results

Non-compartmental parameters for NNZ-2591 in adult participants from the study Neu-2591-HV-001 were evaluated for dose proportionality of exposure after single, first doses and multiple steady-state doses of NNZ-2591 in healthy adult participants. Evaluation of dose proportionality supported the application of the published allometric scaling formula to steady state exposure parameter AUC_{tau} to be matched to adult exposures using body weight normalized dose in mg/kg and apparent steady state clearance in healthy adult participants. The predicted exposures (steady-state AUC_{tau}) were calculated from adult median CLss/F, estimated for morning and evening 12 mg/kg doses on Day 7 in the study Neu-2591-HV-001, for different dose values and body weights from CDC Growth Chart.

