### 5.2.4 Baseline Values

Baseline values that are missing will not be imputed for safety or efficacy measures. For efficacy assessments scheduled to be collected at more than one visit during the Screening/Baseline period, the baseline value will be based on the average of all nonmissing values from assessments conducted prior to the first dose of study drug. For assessments scheduled to be collected once during the Screening/Baseline period, the value from the most recent non-missing assessment prior to the first dose will be used. For safety and other assessments, the value from the most recent non-missing assessment prior to the first dose will be used.

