### 5.3 Definitions

- Age will be derived as the integer value of (informed consent/assent date date of birth + 1)/365.25.
- The age at time of assessment will be derived as the integer value of (date of assessment date of birth + 1)/365.25.

- Body Mass Index (BMI) will be derived as weight in kilograms divided by height in meters squared.
- The change from Baseline measurement for a variable at a particular visit will be derived as the measurement taken at the specified visit minus the baseline measurement. For the Clinical Global Impression Scale Improvement and Caregiver Impression of Change, change from Baseline is the value at the visit.
- Treatment duration in days will be derived as follows: Date of Last Dose Date of First Dose + 1.
- The number of expected doses will be derived as (2\*treatment duration in days)-1, as subjects are expected to receive only their morning dose on the last day of treatment
- The number of doses taken will be derived as the number of doses taken as indicated by the Administration of First Dose CRF and by the Daily Dosing Log CRF for remaining doses, based on completed date and dose fields
- Number of missed doses will be derived based on the number of expected doses the number of doses taken
- Study Day will be derived as Date of Event Date of First Dose (+1 if the date of event ≥ date of first dose)
- Screening/baseline duration in days will be derived as follows: Date of First Dose Date of Screening
- Study duration will be defined as the total number of days in the study (date of last visit date of informed consent + 1).
- History of developmental regression will be determined from the PTHS diagnosis page of the CRF question: "Has the child undergone a regression of skills in the past?" If coded as "yes" the subject is considered as having had a past developmental regression.
- Autism Spectrum Disorder (ASD) diagnosis will be derived from the PTHS diagnosis page of the CRF. If ASD is checked under "confirmation of psychiatric co-morbidities", the subject is considered as having the disorder.
- Bipolar Disorder will be derived from the PTHS diagnosis page of the CRF. If "Bipolar disorders" is checked under "confirmation of psychiatric comorbidities", the subject is considered as having the disorder.

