### 6.3 Demographic and Baseline Characteristics

Demographics variables will include: age, age groups, sex, ethnicity, race, height at baseline, weight at baseline, and BMI at baseline. Age and BMI will be derived as specified in Section 5.3.

Baseline characteristics will include: PTHS Variant Types (as recorded on the CRF), history of developmental regression, Autism Mental Status Exam, seizure types at screening (as recorded on the CRF), presence of co-morbid psychiatric disorders (e.g. Autism Spectrum Disorder (ASD), bipolar disorders, attention deficit disorder, obsessive-compulsive disorder), and Stanford-Binet Intelligence Scales version 5 (SB5) NVIQ standard and z-deviation score or the Bayley Scales of Infant Development – Version 4 (BSID-4) NVDQ for subjects who cannot basal on the SB5 or for whom the SB5 is not developmentally appropriate. If the SB5 was attempted but the child was unable to basal on the assessment, the BSID-4 should be administered. If partial scores for the SB5 are entered in the EDC in addition to the BSID-4, only the BSID-4 scores will be summarized. If the child has complete sets of scores on the SB5 and the BSID-4, the scores for the assessment that was captured at both Screening and EOT will be summarized. If a participant has a complete set of scores for the SB5 and BSID-4 at both Screening and EOT, these cases will be adjudicated by the Sponsor before database lock.

Demographics and baseline characteristics will be summarized for all analysis populations (ITT Population, Safety Population, mITT Population).

Subjects will be evaluated for PTHS at the Screening Visit. The diagnosis and genotype will be documented. PTHS genotypes will be summarized and listed by subject.

History of developmental regression will be determined from the question as reported on the PTHS diagnosis page in the CRF: "Has the child undergone a regression of skills in

the past?" If coded as "yes" the subject is considered as having had a past developmental regression.

The Autism Mental Status Exam (AMSE) will be performed at the Screening Visit. The AMSE is an 8-item observational assessment used to document communicative and behavioral functioning in subjects with ASD. Each question is scored as 0, 1, or 2. The range of the AMSE score is 0 - 14. Higher scores indicate greater severity of autistic symptoms. A question assessing overall impairment is also completed evaluated on a 4-point scale: No impairment, Mild, Moderate and Severe.

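### SAP 7.6 summarises weight and height in children aged 3 to 17 only as raw values and raw change, so absent or slowed weight gain over 13 weeks is not visible in the table

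*SAP*

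**What the plan says.** SAP 7.6 collects weight at the screening visits and all post-baseline visits, and height at Visits 1, 3 and 16. Its summary rule covers every vital sign alike: "Summary statistics for each measurement and the change from baseline will be presented at each post-baseline visit". All measurements are also listed.

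Three other SAP sections fix what that rule produces:

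- SAP 5.3: change is "derived as the measurement taken at the specified visit minus the baseline measurement".
- SAP 5.2.4, on baseline: "For safety and other assessments, the value from the most recent non-missing assessment prior to the first dose will be used".
- SAP 5.3, on body size: "Body Mass Index (BMI) will be derived as weight in kilograms divided by height in meters squared". BMI is then reported only as a baseline characteristic; SAP 6.3 lists "height at baseline, weight at baseline, and BMI at baseline".

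The Addendum does not alter 7.6. Neither document plans a z-score, percentile, growth velocity or expected-gain reference for weight or height.

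On the population, Protocol 8.1 admits "Males or females aged 3 to 17 years at Screening, inclusive". All participants receive the drug (Protocol 7.3) for 91 days (Protocol 9.4.2). Protocol 6.3.1.1 places vital signs in the primary safety endpoint, and Protocol 9.5.1 counts weight among them. Protocol 5.5.1 reports, for studies in adult dogs and juvenile rats, that "there was a decrease in body weight and food consumption in high dose animals", resolving in the four-week recovery period.

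**The concern.** For blood pressure or temperature, no change from baseline is a sensible picture of no effect over 13 weeks. For weight in a growing child it is not, because an untreated child would be expected to gain. A concurrent control group would supply that expected gain. Here nothing does, and the raw-change table invites comparison with zero.

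The effect that could pass unnoticed is specific. A child who stops gaining shows no change, and a child gaining at half the usual rate shows an increase. Reduced food intake would act in that direction, and the animal findings give reason to look for it. At stake is whether a primary safety table can be interpreted for one of its variables.

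**Working it through.** The documents give no figure for growth or expected weight change, so there is no stated figure to reproduce. The check is a reading of the text plus an illustration on assumed values.

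**Inputs.** Treatment duration is 91 days (Protocol 9.4.2). Growth velocity is assumed at 2 to 5 kg per year. The reference SD of weight for age is assumed at 2.5 to 10 kg. Neither assumption comes from the documents.

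**What the planned table shows.** Expected gain = velocity × 91/365.25.

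| Assumed velocity (kg/year) | Expected gain (kg) | Shown if gain stops (kg) | Shown at half rate (kg) |
|---|---|---|---|
| 2 | 0.50 | 0.00 | +0.25 |
| 3 | 0.75 | 0.00 | +0.37 |
| 5 | 1.25 | 0.00 | +0.62 |

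Widening the velocity to 1.5 to 6 kg per year gives an expected gain of 0.37 to 1.49 kg and a half-rate display of +0.19 to +0.75 kg.

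**What a z-score would show.** With exact age, the shift for a fully stalled child is −(expected gain)/(reference SD).

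| Velocity (kg/year) | SD 2.5 kg | SD 5 kg | SD 10 kg |
|---|---|---|---|
| 2 | −0.20 | −0.10 | −0.05 |
| 3 | −0.30 | −0.15 | −0.07 |
| 5 | −0.50 | −0.25 | −0.12 |

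The shift has the right sign, but it is small.

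**Which age to use.** SAP 5.3 defines age at assessment as an integer number of years. Only about 91/365.25 = 25% of children have a birthday during treatment. For the other 75% the reference would not move, so a stalled child would show a z-score change of zero, which repeats the problem. A child who does have a birthday jumps a full year up the reference. Assuming 2.5 kg per year and an SD of 3 kg, a normally growing child with a birthday would show (0.62 − 2.5)/3 = −0.63. SAP 9.2.16 already has a suitable age in months: (date of assessment − date of birth + 1)/30.4375.

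**Whether a fixed z-score cut-off would work.** Take a fall of 0.25 as an example. A full stop reaches it only if the reference SD is at most gain/0.25: 0.50/0.25 = 2.0 kg, 0.75/0.25 = 3.0 kg, or 1.25/0.25 = 5.0 kg. At larger SDs stalled children would be missed, and half-rate growth would need SDs half as large. A count of participants with no weight gain avoids this.

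**The case against.** The strongest defence is that the table is not the only route to a weight problem. SAP 5 adds median, minimum and maximum, and every weight is listed. Nurses weigh participants and ask about oral intake (Protocol 9.1), and the diary records intake changes (Protocol 9.5.10). Vital-sign changes judged clinically significant are recorded as adverse events (Protocol 10.5). The DSMC receives raw listings (SAP 4). SAP 7.6 tests nothing against zero. All of this is true, and actual weight loss would be seen. But none of these routes standardises for growth, and a flat weight offers no abnormal value to prompt an investigator's judgement.

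A reader might infer that a growth signal was seen in animals and that this trial will miss it. The documents do not support that. Protocol 5.5.1 describes a reversible high-dose decrease in body weight and food consumption. The dogs were adult, and the 13-week juvenile-rat study is said to show no drug-related adverse effects. Protocol 6.2.0 does put the juvenile-rat NOAEL at 200 mg/kg/day, while 13-week dosing went up to 400 mg/kg/day (5.5.1). The documents do not say what set that level. The animal data justify attention to weight, not a claim of impaired growth.

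A reader might also infer that the table would lead the sponsor to conclude there is no effect on weight. With no test planned and several other sources of information, that goes too far.

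It also stands that the growth rates are assumptions, that the documents give no growth data for Pitt-Hopkins syndrome, and that z-scores in 10 to 20 uncontrolled participants cannot separate a drug effect from natural variation.

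**Conclusion.** The point holds in a limited form. As planned, the weight and height summaries cannot distinguish normal growth from slowed or absent growth, because they have neither a control arm nor an age- and sex-specific reference. On the assumed 2 to 5 kg per year, the hidden shortfall for a child who stops gaining is about 0.50 to 1.25 kg over 91 days. This is a gap in how a primary safety variable is summarised. It does not affect trial conduct, and the documents do not show that any harm to growth exists. The conclusion that zero is the wrong reference rests only on participants being expected to grow; the sizes rest on the assumed velocities and reference SDs.

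**What to change.** Amend SAP 7.6 before database lock, since SAP 5 treats analyses added later as exploratory:

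- Add the change from baseline in age- and sex-specific weight z-score at each post-baseline visit.
- Add the change in height and BMI z-score at end of treatment only, because height is not measured at any other post-baseline visit.
- Name the CDC growth reference and the conversion to z-scores. Appendix A took body weights from "the Centers for Disease Control and Prevention (CDC) Growth Individual charts", by month of age and gender. It used weight only, so the height and BMI references must be specified as well.
- Use exact age in months at assessment, as in SAP 9.2.16, not the integer-year age in SAP 5.3.
- Add a count of participants with no weight gain from baseline at end of treatment. Do not rely on a fixed z-score drop such as 0.25.
- Keep the kg and cm summaries in the tables, so that actual weight loss remains directly visible.

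The cost is SAP wording and a short derivation; no new data are needed. The limits are that expected shifts are small (about −0.05 to −0.50 for a fully stalled child on the assumed values) and that the result is descriptive at this sample size.
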